- a. Assessing the effect of the ONS administration on nutritional status, which includes: energy and macronutrient intake, body weight, body mass index (BMI), mid-upper arm circumference (MUAC), muscle mass.
- b. Assessing the effect of giving ONS on physical function, namely grip strength.
- c. Assess the effect of the ONS administration on the patient's inflammatory response, which includes: CRP, neutrophils, lymphocytes, neutrophil/lymphocyte ratio (NLR) and IL-6.

RESEARCH METHODS

A. Research Design

This research is an experimental study using a Double-Blinded Randomized Controlled Trial design, with the intervention group receiving ONS containing immunonutrients with a composition consisting of purple yam flour, white egg flour, whey protein, olive oil, omega-3 powder, sugar, and creamer. In contrast, the control group received a standard ONS (iso-calorie) placebo with a composition of powdered skim milk, coconut oil, sugar, maltodextrin, and creamer. Each group received two packs of ONS/day @ 57 grams, brewed into 200 ml of formula with an energy content of ± 500 kcal for three weeks.

B. Population/Subject/Sample

The population in this study were MPA patients at RSUP [name], while the research subjects were these patients who met the following inclusion and exclusion criteria.

1. Inclusion criteria
 - a. Subjects diagnosed with advanced stage MPA (stages 3 and 4) who received radiotherapy or chemoradiotherapy, both as concurrent and adjuvant therapy.
 - b. Subjects aged 18-80 years.
 - c. Can consume food through a nasogastric tube (NGT) or orally.
 - d. Willing to participate in the research by signing informed consent. However, if the patient's general condition is terrible, the family is willing to sign an informed consent and help with the research.
2. Exclusion criteria
 - a. The subject has a milk or egg allergy
 - b. Subjects with comorbid renal impairment
 - c. Subjects with poor nutritional status with $BMI < 17.0 \text{ kg/m}^2$
 - d. Subject could not stand for weighing
3. Dropout criteria:
 - a. Subject died
 - b. Subjects withdrew from the study
 - c. Average ONS consumption $< 75\%$

The size of the study subjects was determined based on parameters of protein intake because one of the significant differences in the intervention and control formulas was the protein

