content (Arnold and Richter, 1989; Dahlan, 2013). The minimum number of subjects in this study was 22 subjects, with an additional 20% of 5 subjects, so the number of research subjects in each group was 27 or 54 subjects.

C. Location and Time of Research

The location of this research will be carried out at dr. Sardjito Yogyakarta, with research time, will be carried out for 14 months, starting from March 2022 to April 2023.

D. Research Parameters

This study has several research parameters, which include nutritional status in the form of changes in body weight, BMI, MUAC, body composition (muscle mass), and albumin; handgrip strength as physical function; and inflammatory response in the form of CRP, complete blood profile (leukocytes, neutrophils, lymphocytes, neutrophil/lymphocyte ratio).

E. Materials and Procedures

1. Research Materials

Materials for the manufacture of ONS immunonutrients

- 1) Purple sweet potato flour made from purple sweet potato flour of the Antin 3 variety
- 2) Ovobel white egg flour
- 3) Whey protein isolate 90
- 4) Bertolli brand virgin olive oil
- 5) Omega-3 powder from Novotech Nutrition USA
- 6) Powdered sugar obtained from refined sand from the Gulaku brand
- 7) Fiber Creme brand creamer

Materials for making standard ONS:

- 1) Low-fat milk brand Tropicana Slim
- 2) Barco brand coconut oil
- 3) Powdered sugar obtained from refined sand from the Gulaku brand
- 4) Fiber Crème brand creamer
- 5) Maltodextrin

2. Research Procedures

a. Preparation of Intervention Substances (ONS Immunonutrient formula and standard ONS)

Making ONS formulas containing either immunonutrients or standard ONS is done by mixing all the ingredients using a mixer with the amount of each ingredient according to the predetermined amount. The main ingredient in this formula is purple sweet potato flour, made by drying fresh purple sweet potatoes which have been blanched beforehand.

b. Clinical Trials

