For the measurement of research parameters in the form of nutritional status, it relatively does not pose a medical risk or trauma to the subject; while taking blood samples there is a risk in the form of phlebitis but this can be prevented by handling blood sampling, by a competent laboratory assistant. The product consumed by the subject was in the form of ONS or liquid food (such as milk) dense in nutrition (high in energy, high in protein, containing immunonutrients in the form of anthocyanin and omega 3), which was recommended by ESPEN as nutritional support for cancer patients undergoing radiotherapy. In addition, the consumption of products provided in the form of standard ONS or those containing immunonutrients carries a risk of digestive tract disorders, such as diarrhea, bloating, or constipation. If this happens, the subject will be referred to the doctor in charge of the study (DPJP or a radiation oncologist/dr. Sp. Onk. Rad) for examination and medication, the handling costs are the full responsibility of the researcher

F. Design of Data Processing/Analysis

The research data results were analyzed descriptively in the form of average \pm standard deviation if the data were normally distributed or median if the data were not normally distributed. The pre and post-test dependent variable data in each treatment and control group will be analyzed using a paired t-test if the data is normally distributed. Still, if the data is not normally distributed, it will be analyzed using Wilcoxon. As for the analysis of the difference between the pre and post test data then comparison between the control and intervention groups was carried out with the Independent t-test if the data was normally distributed, but if it was not normal, then it was analyzed using Mann Whitney.

G. Research Ethics

This research has received permission for ethical research feasibility from the Health Research Ethics Commission, Faculty of Medicine, Public Health and Nursing, Universitas Gadjah Mada Yogyakarta Indonesia with the number KE/FK/0996/EC/2021. Then before participating in the research, there will first be an explanation of the research's aims and objectives, the course of the research, and the benefits and risks that prospective research subjects may face. If the subject understands and agrees to participate in the study, the subject is asked to sign the informed consent that has been provided.

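### Section F compares arms on the raw pre-post difference with no baseline covariate: the test is valid, but ANCOVA on a scale named in advance would be more precise for outcomes that track only moderately

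*Combined protocol and SAP*

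**What the plan says.** Section F (Design of Data Processing/Analysis) plans within-arm paired tests and then a between-arm test. The between-arm variable is the change score: "the analysis of the difference between the pre and post test data". If it is normal, "comparison between the control and intervention groups was carried out with the Independent t-test if the data was normally distributed". For all other outcomes a rank test takes its place, and the clause reads: "but if it was not normal, then it was analyzed using Mann Whitney". The protocol mentions no regression, baseline covariate, transformation or scale chosen in advance, and Section F mentions no confidence interval.

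The outcomes are mixed in kind. The specific goals list "energy and macronutrient intake, body weight, body mass index (BMI), mid-upper arm circumference (MUAC), muscle mass", then grip strength, then "CRP, neutrophils, lymphocytes, neutrophil/lymphocyte ratio (NLR) and IL-6". Section D (Research Parameters) adds albumin and words the inflammatory panel as CRP and "complete blood profile (leukocytes, neutrophils, lymphocytes, neutrophil/lymphocyte ratio", without IL-6 or intake.

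On size, Section B states: "The size of the study subjects was determined based on parameters of protein intake". It continues: "The minimum number of subjects in this study was 22 subjects", to which 20% is added. I read the 22 as per group, because 22 + 5 = 27 is the stated group size.

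**The concern.** A change score does use the baseline, but with its coefficient set at 1. If the real slope of the week-3 value on baseline is well below 1, subtracting the whole baseline adds noise. ANCOVA estimates that slope instead. With 22 evaluable subjects per arm, the difference can be worth several subjects per arm, from measurements that a pre-post analysis needs anyway.

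For skewed markers there are two further points. Mann-Whitney on raw change also leaves the baseline slope at 1. And the method is settled only after a normality check on trial data, so the effect to be reported is not fixed beforehand.

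**Working it through.** **The plan's own figure.** 22 × 0.20 = 4.4, rounded up to 5; 22 + 5 = 27 per group; 2 × 27 = 54. The addition reproduces. The base of 22 cannot be reproduced, because no alpha, power, difference or SD is given. If two-sided 5% and 80% power are assumed, it corresponds to (1.960 + 0.842) × √(2/22) = 0.84 SD.

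**Assumed inputs.** Two-sided 5%; n = 22 per arm; pre-post correlation ρ from 0.3 to 0.95; k = SD_post/SD_pre of 0.75, 1 or 1.5. None of ρ, k or the SDs is in the documents.

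**Variance, roughly normal data.** Up to a common factor:
- Var(change) = 1 + k² − 2ρk
- Var(ANCOVA) = k²(1 − ρ²) × [1 + 1/(2n − 4)], averaged over 1:1 randomisations; at n = 22 the factor is 1 + 1/40 = 1.025.

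With k = 1 the ratio is 1.025 × (1 + ρ)/2. At ρ = 0.5 this is 1.025 × 0.75 = 0.769, and 22/0.769 ≈ 29.

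| ρ | 0.3 | 0.5 | 0.7 | 0.9 | 0.95 |
|---|---|---|---|---|---|
| ANCOVA/change, k = 1 | 0.67 | 0.77 | 0.87 | 0.97 | 1.00 |
| 22 per arm worth about (k = 1) | 33 | 29 | 25 | 23 | 22 |
| k = 1.5 | 0.89 | 0.99 | 1.02 | 0.80 | 0.56 |
| k = 0.75 | 0.47 | 0.53 | 0.57 | 0.52 | 0.41 |

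**Worst average cost.** Since (1 + k² − 2ρk) − k²(1 − ρ²) = (1 − ρk)² ≥ 0, the ratio cannot exceed 1.025 (1.020 at 27 per arm), reached when ρk = 1.

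**Power, normal data, k = 1, effect 0.8 SD (simulated).** At ρ = 0.3/0.5/0.7 the change t-test has 59/74/92% and ANCOVA 76/84/95%. At effect 0.4 SD and ρ = 0.9 the figures are 83% and 84%.

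**A single trial with a 2-SE baseline imbalance.** The ANCOVA variance factor is about 1 + 4/42 = 1.095 (simulated 1.098), a cost of about 10%. With k = 1 the change score is then conditionally biased, so mean squared error is the fair comparison: 1.098(1 + ρ)/[(1 + ρ) + 4(1 − ρ)] = 0.35/0.47/0.64/0.91/1.00 across the five values of ρ. If ρk = 1 there is no such bias, and the 10% is a net loss.

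**Validity.** At 22 per arm, simulated type I error was 4.8–5.3% for the change t-test on normal data. For the rule that picks the test by normality it was 4.9–5.4% on normal data and 4.5–5.4% on lognormal data.

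**Skewed markers (simulated, ρ = 0.5).** Two assumed structures give opposite answers.
- *Constant-ratio effect on lognormal data* (equal log-SDs of 0.5 to 1, a reduction of 0.8 log-SD). Mann-Whitney on raw change has 49–77% power, depending on skewness and on whether both arms share a rise; log-ANCOVA has 83–84%. A t-test on log change has 73–74%, so without a shared rise part of the gain comes from logs and not from baseline adjustment. Raw-scale ANCOVA at log-SD 1 has 62%, against 50% for Mann-Whitney without a shared rise and 76% with one.
- *Additive change on a lognormal baseline* (effect 0.8 SD of change; log-SD 0.5 with ρ about 0.98, or log-SD 0.3 with ρ about 0.75, in place of ρ = 0.5). The planned tests have 71–74%, log-ANCOVA about 58–66% and rank ANCOVA 56–66%.

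**The case against.** The strongest case against is that the planned test is valid, matches Section D, which defines the nutritional parameters as changes, and holds its type I error. Every magnitude above also depends on inputs that the documents do not supply.

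Most of this stands. The range runs from about 11 extra subjects per arm to none, and which outcomes track closely is a judgement. Weight, BMI and MUAC over three weeks plausibly sit at the high end, where nothing is gained. Section D's wording is no obstacle: regressing change on group and baseline gives the same group coefficient as regressing the week-3 value.

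A second objection also stands. The 2.5% bound covers raw-scale ANCOVA against the change t-test under normality. It says nothing about log-ANCOVA, which can lose roughly 6 to 15 points when change is additive on a skewed baseline. Rank ANCOVA can lose there too. The documents do not say which structure applies, so logs for the inflammatory markers must be conditional.

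Third, Section B counts subjects with average consumption below 75% as dropouts, so the set compared may not be the set randomised. That is a separate issue. ANCOVA does not repair it, and the validity stated here refers to the groups as randomised.

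**Conclusion.** The point holds as an efficiency improvement. With equal SDs and 22 per arm, ANCOVA cuts variance by about 33%, 23% and 13% at ρ = 0.3, 0.5 and 0.7, by about 3% at 0.9, and not at all at 0.95. With unequal SDs it ranges from a large gain to a 2% loss in the cells shown.

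A reader might infer three stronger things that the documents do not support:
- *That the planned comparison is biased or invalid.* It is unbiased over randomisation, and its simulated type I error is close to nominal.
- *That ANCOVA improves every outcome on any scale.* It gains nothing at very high tracking, raw-scale ANCOVA can fall below Mann-Whitney for strongly skewed markers, and log-ANCOVA can fall below the planned tests when change is additive.
- *That the trial is shown to be underpowered.* No power, effect or SD is stated, so this cannot be judged.

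**What to change.** In Section F, replace the between-arm test by one model per outcome: week-3 value on group and baseline value. Test the group term and report the adjusted difference with a 95% CI. Name the scale for each outcome before unblinding, in place of a test chosen after a normality check. Section E releases the product key only after the analysis, so in practice this means before outcomes are compared by product code.

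- Raw scale: weight, BMI, MUAC, muscle mass, grip strength, albumin.
- CRP, IL-6, NLR and cell counts: logs of both baseline and week-3 values if effects are expected to be proportional, with that expectation stated. Name rank-based ANCOVA as back-up with a stated trigger, such as values below the assay limit.
- Energy and macronutrient intake: fix raw or log in advance from the pooled baseline distribution.

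The cost is a few sentences and one degree of freedom per model (41 instead of 42 at 22 per arm). On the raw scale under normality, the variance cost against the change t-test is at most about 2.5% on average, and about 10% in a single trial with a 2-SE imbalance. That bound does not extend to the logged markers, whose effects would be reported as ratios. No new measurement is needed where baseline and week-3 values are already collected. Section D should confirm this for intake and IL-6, which appear only among the specific goals.

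### Section F leaves the between-arm test to an undefined normality check on raw pre-post differences, so the quantity tested is not fixed and no effect estimate is specified

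*Combined protocol and SAP*

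**What the plan says.** Section F (Design of Data Processing/Analysis) is the whole analysis plan, and one condition drives all of it.

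- **Between arms.** The quantity is "the analysis of the difference between the pre and post test data then comparison between the control and intervention groups", and the test is chosen "with the Independent t-test if the data was normally distributed, but if it was not normal, then it was analyzed using Mann Whitney".
- **Within arms.** Pre and post values "will be analyzed using a paired t-test if the data is normally distributed"; "if the data is not normally distributed, it will be analyzed using Wilcoxon".
- **Description.** The summary is the mean with "standard deviation if the data were normally distributed or median if the data were not normally distributed". No measure of spread goes with the median.

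No section names a normality test, a threshold, or whether raw values, changes, each arm or the pooled sample are checked. None names a transformation, a baseline-adjusted model, an effect measure or a confidence interval. Application outcome by outcome is the natural reading of a single rule, though it is not written out.

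The rule covers the nutritional and grip-strength outcomes and, in Section D, the "inflammatory response in the form of CRP, complete blood profile (leukocytes, neutrophils, lymphocytes, neutrophil/lymphocyte ratio"). The specific objectives add IL-6 and dietary intake, which Section D does not list.

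**The concern.** The t-test addresses a difference in means; Mann-Whitney addresses whether values in one arm tend to exceed those in the other. If the data choose between them, the question answered is not fixed in advance and may differ from one outcome to the next. Because the check is undefined, two competent analysts could report different tests on the same data. The within-arm rule has the same gap: a paired t-test needs only the differences to be near normal, and Section F does not say that the differences are what is checked.

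A p-value with two medians does not show what effect a null result excludes. That matters with 22 to 27 patients per arm and with inflammatory response as a stated objective.

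CRP, NLR and cell counts are positive and plausibly right-skewed. Raw differences in such markers are dominated by patients with high values, so power may be lost whichever branch is taken.

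**Working it through.** **The plan's own figure.** Section B: "The minimum number of subjects in this study was 22 subjects, with an additional 20% of 5 subjects". 22 × 0.20 = 4.4, rounded up to 5; 22 + 5 = 27 per arm; 2 × 27 = 54. This reproduces. The plan gives no error rate or power for the Section F rule, so those are simulated.

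**Assumptions, none from the documents.** Two-sided 5% tests; Shapiro-Wilk at 5% in each arm as the normality check; log-normal markers unless stated. Section F gives no alpha, check or distribution.

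**Step 1: which test is chosen** (22 per arm unless stated).
- Truly normal data: Mann-Whitney in about 10% of trials.
- Moderately skewed change (gamma, shape 4): t-test in about 46%.
- Log-normal marker, 22 or 27 per arm: t-test in 42–57% of trials at log-SD 0.5, 8–24% at 0.8 and 0.5–4% at 1.2.

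The choice thus depends on the sample for mild skew and is nearly always Mann-Whitney for strong skew. It is not immaterial: over 18 log-normal scenarios (22 or 27 per arm; log-SD 0.5, 0.8, 1.2; correlation 0.3, 0.5, 0.7), the two tests disagree on significance in 11–28% of trials with a real effect and in 3–5% under the null.

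**Step 2: type I error of the rule.** It is 4.0–5.4% over those 18 scenarios. For gamma change, runs of 4,000 trials gave about 6%; a run of 40,000 gave 5.3% (Monte Carlo standard error √(0.053 × 0.947 / 40,000) ≈ 0.1 points).

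**Step 3: power, CRP-like data.** 22 per arm, log-SD σ = 1.0, 1.5-fold rise in both arms, treatment ratio 0.5, pre-post correlation ρ.

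| Analysis | ρ = 0.5 | ρ = 0.7 |
|---|---|---|
| Section F rule, raw change | 52% | 73% |
| Always Mann-Whitney, raw change | 53% | 73% |
| t-test on log change, unadjusted | 61% | 82% |
| ANCOVA on log scale | 71% | 87% |

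Closed-form check, with SE = SD × √(2/22) and effect ln 2 = 0.693:
- Log change, SD = σ√(2(1−ρ)): 1.000 and 0.775; SE 0.302 and 0.234; effect/SE 2.30 and 2.97; power 61% and 83%.
- ANCOVA, residual SD = σ√(1−ρ²): 0.866 and 0.714; SE 0.261 and 0.215; effect/SE 2.65 and 3.22; power 74% and 88%. This is slightly above the simulation because the formula ignores chance baseline imbalance.

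The rule matches always using Mann-Whitney to within about a point. The gap to log-scale ANCOVA is 71 − 52 = 19 points and 87 − 73 = 14 points.

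**Step 4: where the gap arises.** Take 22 per arm, log-SD 0.8, ρ = 0.5, no common rise, and an effect sized for about 80% ANCOVA power. The rule has 47.8%, the t-test on log change 66.4%, and log-scale ANCOVA 77.3%. The log scale contributes 66.4 − 47.8 = 18.6 points and baseline adjustment 77.3 − 66.4 = 10.9. Over all 18 scenarios the rule has 36–59% and log-scale ANCOVA 75–79%.

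**Step 5: is a log scale alone enough?** With log-SD 0.35, a 1.5-fold rise and ratio 0.8, at ρ = 0.5 and 0.7, the rule has 60% and 81%, the unadjusted t-test on log change 55% and 77%, and log-scale ANCOVA 65% and 83%. Log change without adjustment can do worse than the existing rule, even for exactly log-normal data.

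**Step 6: normal outcomes.** With 22 per arm and ρ = 0.5 and 0.7, the rule has 66.5% and 70.2%, and raw-scale ANCOVA 77.2% and 76.3%.

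**The case against.** It can fairly be said that choosing between a t-test and Mann-Whitney after a normality check is common practice and does little measurable harm. Much of this stands. A reader might infer any of the following, and none is supported.

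- *The rule inflates false positives.* It barely does (Step 2). Larger inflation would need the analyst to report whichever test is significant, which Section F does not permit. The product code is also withheld until the analysis is done (Section E, Clinical Trials). That limits steering towards the intervention, though not towards significance in general.
- *The normality check causes the power loss.* It does not (Step 3). Deleting the check while keeping raw differences would recover almost nothing.
- *For CRP the choice of test is a coin toss.* In the CRP-like scenario the t-test is picked in only about 5–8% of trials. A near-even split arises with milder skew.
- *Disagreement between the tests shows how often the rule changes the verdict.* It shows only that the two tests are not interchangeable.
- *The missing interval is a fault of the non-normal branch.* No interval is specified on either branch.

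The power gain also depends on spread, correlation and time trend, none of which the documents give. It is small for mildly skewed markers: 5 and 2 points in Step 5.

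What the objection does not answer is that the target is undefined and no estimate is promised. Both are read directly from Section F and need no distributional assumption.

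**Conclusion.** The concern holds as a failure to fix the analysis in advance. Section F leaves the tested quantity to an undefined check and commits to no between-arm estimate or interval. There is no material inflation of type I error, and the check costs almost no power.

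The power loss is a separate consequence of using raw differences with neither a log scale nor baseline adjustment. For a strongly skewed marker it may be sizeable, at 14 to 19 points under the CRP-like assumptions, and for mildly skewed markers it is small. The direction favoured log-scale ANCOVA in every log-normal effect scenario run; the size rests on assumed distributions and should not be read as a property of this trial's CRP data. The improvement is worth making because it costs only wording.

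**What to change.** Delete the normality rule from Section F and name one between-arm analysis per outcome before any outcome data are analysed. Code release is too late as a deadline, because the protocol places it after the analysis.

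- **Weight, BMI, MUAC, muscle mass, albumin, grip strength and intake:** ANCOVA of the post value adjusted for baseline, raw scale; mean difference with 95% CI. The treatment effect is the same as from ANCOVA on the change, so Section D's wording about changes is still served.
- **CRP, IL-6, NLR, leukocytes, neutrophils and lymphocytes:** the same model on the log scale; geometric mean ratio with 95% CI. State in advance how any value below an assay limit is handled; the documents give no limits.
- **Sensitivity analysis, labelled as such:** Mann-Whitney on the change, with the Hodges-Lehmann difference and its interval.
- **Description:** median with quartiles in both arms for skewed outcomes.

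The cost is SAP wording, with no extra patients. IL-6 and intake need confirming as measured outcomes, since they appear in the objectives but not in Section D. The downside is some loss of efficiency if a marker is far from log-normal.
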